### 8.2 Summarization of safety data:

This is a low-risk interventional study, and the FDA has determined it to be a non-significant risk device study. As a result, no data and safety monitoring board is planned. Adverse events will be regularly assessed, and those considered likely attributable to study procedures will be documented, as will all SAEs. Within each treatment arm, the frequency and percentage of study-related adverse events and SAEs will be tabulated and reported by grade, system organ-class, and preferred term. Any study-related adverse events will be summarized as those leading to a specific intervention, those leading to study discontinuation, and by severity. Any SAEs will be reported similarly.

### 8.3 Key covariates:

Key covariates to include in the data analysis model are based on established predictors in this setting: time post-stroke (number of days from stroke onset to randomization), severity of impairment (arm motor FM score at Baseline Visit), age, and enrollment site. Stroke subtype (ischemic vs. intracerebral hemorrhage) will also be included as a covariate.

#### Primary outcome measure:

The primary outcome measure is the within-subject change in arm motor FM score from Baseline Visit to 30 Day Follow Up Visit ( $\Delta_{FM}$ ). The higher the FM score, the better the outcome. Hence, with therapy, we anticipate the primary outcome measure will be an increase in FM score for each subject.

#### Non-inferiority margin:

The trial seeks to establish comparable efficacy based upon a non-inferiority margin of 2.05 (a value that is less than half the minimal clinically important difference for change in FM score) for the difference between the two treatment groups in the mean within-subject change in FM score from Baseline Visit to the 30 day Follow Up Visit. We consider a maximum of 30% smaller mean  $\Delta_{FM}$  in the telerehabilitation group (as compared to the in-clinic treatment) to be clinically acceptable to consider it to be non-inferior. Based upon preliminary data, the mean  $\Delta_{FM}$  for the telerehabilitation group is expected to be 4.80 points. Thus, if the assumed mean  $\Delta_{FM}$  is 6.85 points in the in-clinic group, a reduction up to 30% (2.05 points) to 4.80 points in the telerehabilitation group would be concluded to be comparably efficacious.

#### Primary efficacy analysis:

The primary analysis of the  $\Delta_{FM}$  will be conducted using an analysis of covariance (ANCOVA) model, adjusting for days from stroke onset to randomization, FM score at Baseline Visit, age, and enrollment site. The lower bound of the 95% confidence interval for the difference in  $\Delta_{FM}$  between treatment groups will be used to assess comparable efficacy. If the lower bound of the 95% confidence interval for the difference in  $\Delta_{FM}$  between groups (i.e.,  $\Delta_{FM}$

for the telerehabilitation group -  $\Delta_{FM}$  for the in-clinic group) is greater than -2.05, then we would declare telerehabilitation to be non-inferior.

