### **5.2. Randomization**

A web-based central randomization system developed by StrokeNet National Data Management Center (NDMC) and installed on the WebDCU™ Telerehabilitation Study website. Subjects will be assigned to one of the treatment groups according to the randomization scheme developed at the NDMC. Randomization will be done centrally using the WebDCU™ for all subjects entered in the trial. Covariate-adaptive randomization will be used to insure that values for (1) number of days post-stroke at time of randomization (2) FM score at the baseline visit, and (3) site are balanced across the two treatment groups.

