## 8. STATISTICAL CONSIDERATIONS, DATA ANALYSIS AND DATA MONITORING

In the study, populations used for testing comparable efficacy, the non-inferiority margin proposed for determining comparable efficacy, the statistical procedures used for summarizing and testing the primary and secondary comparable efficacy endpoints, and sample size justification for the proposed study. All analyses are two-tailed and use  $\alpha=0.05$ .

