**8.4 Secondary efficacy analyses:**

Two secondary endpoints examining change in motor status will be examined. Each examines treatment effects along an independent dimension, and will be analyzed as above. These are

- Within-subject change in Box & Blocks score from the Screening Visit to the 30 Day Follow Up Visit
- Within-subject change in Stroke Impact Scale-Hand Domain score from the Baseline Visit to the 30 Day Follow Up Visit

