### 13.2. Inclusion/Exclusion Criteria:

#### Inclusion criteria

1. Age  $\geq 18$  years at the time of randomization
2. Stroke that is radiologically verified, due to ischemia or to intracerebral hemorrhage, and with time of stroke onset 4-36 weeks prior to randomization
3. Arm motor FM score of 22-56 (out of 66) at both the Screening Visit and Baseline Visit
4. Box & Block Test score with affected arm is at least 3 blocks in 60 seconds at the Screening Visit
5. Informed consent signed by the subject
6. Behavioral contract signed by the subject

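### Section 8.3 puts stroke subtype in the analysis model, the primary ANCOVA leaves it out, and nothing says which list governs the non-inferiority test

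*Combined protocol and SAP*

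**What the plan says.** The combined protocol and SAP describes the covariates in two places within section 8.3.

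- The key-covariates paragraph opens "Key covariates to include in the data analysis model are based on established predictors in this setting". It lists time since stroke, "severity of impairment (arm motor FM score at Baseline Visit), age, and enrollment site". A separate sentence follows: "Stroke subtype (ischemic vs. intracerebral hemorrhage) will also be included as a covariate".
- The paragraph headed Primary efficacy analysis specifies an ANCOVA on change in FM score, "adjusting for days from stroke onset to randomization, FM score at Baseline Visit, age, and enrollment site". Subtype is not mentioned. Non-inferiority is declared if the lower limit of the 95% confidence interval for telerehabilitation minus in-clinic exceeds -2.05.

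Section 8.4 passes the question on to the two secondary motor endpoints, Box & Blocks and SIS-Hand: "Each examines treatment effects along an independent dimension, and will be analyzed as above". The models written out in section 8.5 (stroke knowledge, risk factors, compliance, PACES, OPS) also omit subtype.

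Subtype varies in this population, because inclusion criterion 2 admits both kinds: "Stroke that is radiologically verified, due to ischemia or to intracerebral hemorrhage". It is not one of the factors balanced by the randomization in section 5.2, which are days since stroke, baseline FM and site.

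**The concern.** The trial's conclusion rests on one confidence limit from one model, and the text supports two models. One statistician could program four covariates and cite the primary-analysis paragraph. Another could program five and cite the key-covariates paragraph. Because subtype is left to chance at randomization, the two limits will differ somewhat in any given trial. If the limit falls near -2.05, the verdict could depend on which paragraph was followed, and that choice could be made after the results are known. Fixing the model in advance is meant to prevent this.

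**Working it through.** **The two lists side by side**

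| Covariate | Key covariates (8.3) | Primary ANCOVA (8.3) |
|---|---|---|
| Time since stroke | yes | yes |
| Baseline FM | yes | yes |
| Age | yes | yes |
| Site | yes | yes |
| Stroke subtype | yes | not listed |

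**The plan's own sample size.** Inputs from the sample-size paragraph are margin 2.05, SD 4.0, 80% power and a two-sided 95% interval. A true difference of 0 is assumed, since the paragraph does not state one.

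- Normal approximation: n per arm = 2 × [4.0 × (1.960 + 0.842) / 2.05]² = 59.8, so 60. The noncentral t version gives 61. The plan has 62.
- Power at 62 per arm by noncentral t is 80.8%. Dropout: 124 / 0.80 = 155, as stated.
- This calculation uses no covariates, so the choice of list cannot alter N. The 80.8% is a two-sample figure, not the power of either ANCOVA. With uninformative covariates, simulated ANCOVA power is slightly lower, about 78% to 80%.

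**Degrees of freedom.** Section 12 assumes 8 sites. Four covariates: 124 - 2 - 3 - 7 = 112. With subtype: 111.

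**How far apart the two limits fall.** The documents give no hemorrhage share, subtype effect or explained variance. Assume 20% share, 20% of variance explained by the other covariates, and an effect of 0, 1 or 2 FM points.

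1. Residual SD = 4.0 × √0.8 = 3.58. Standard error of the difference = 3.58 × √(2/62) = 0.643.
2. At zero true difference the lower limit centers on -1.98 × 0.643 = -1.27. That is 0.78 points, or 1.21 standard errors, above -2.05. Its density at the margin is 0.192 / 0.643 = 0.30 per point.
3. The chance difference between arms in hemorrhage share has SD √(2 × 0.2 × 0.8 / 62) = 0.072. A 2-point effect turns this into 0.144 points.
4. Adding any term also moves the limit by chance. In simulation the SD of that movement is about 0.07 points with no subtype effect and uninformative other covariates; scaled by √0.8 it is 0.063.
5. Combined SD of the shift at 2 points = √(0.144² + 0.063²) = 0.157. Mean absolute shift = 0.798 × 0.157 = 0.125. Opposite verdicts ≈ 0.30 × 0.125 = 3.7%.
6. The same steps give about 2.3% for 1 point and 1.5% for no effect.

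**Simulation** (62 per arm, total SD 4.0, 8 sites, complete data, multiple imputation not modeled). Opposite verdicts with 20% of variance explained and zero true difference, over hemorrhage shares of 10% to 30%:

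| Subtype effect | Opposite verdicts |
|---|---|
| 0 points | 1.3% |
| 1 point | 1.7% to 2.2% |
| 2 points | 2.7% to 4.3% |

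A separate run at 20% share gave 1.4% (no effect) and 3.5% (2 points), in line with the hand calculation. The highest value in the main grid, 8.3%, needs a 30% share, a 3-point effect and other covariates that explain nothing. If the true difference is -1 rather than 0, disagreement is more frequent: 6.7% at 20% share, 2 points and 20% explained.

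**Error rate.** At a true difference of -2.05, either model alone declares non-inferiority in 2.4% to 2.6% of trials. Taking whichever model is favorable gives 2.7% to 3.5%.

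**The case against.** The strongest reply is that specific text overrides general text. The primary-analysis paragraph defines the model, and the section 8.5 models that spell out their covariates also leave subtype out, so the subtype sentence is the outlier. This is a reasonable reading, but the documents do not state it, and under it the subtype sentence would have no effect anywhere. The 8.5 models are also weak evidence, because they drop baseline FM as well and so do not follow the 8.3 list in other respects. What stands is that correcting the key-covariates paragraph is a legitimate repair, and that the documents do not prove the omission in the primary model to be the error.

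A second reply is that the effect is small and the percentages depend on assumed inputs. That also stands. Even a subtype with no effect gives about 1.3% disagreement at 20% explained variance, so part of the figure is what changing any model term would produce.

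A reader might go further and infer that the primary analysis is biased, or that the trial is mis-sized. The documents support neither. Both covariate sets are fixed before randomization, either ANCOVA is valid if prespecified, and N was derived without covariate adjustment.

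**Conclusion.** The conflict is real and lies in current text: two stated rules for the decisive model, with nothing to rank them. Its likely numerical effect is small. With no true difference, 20% hemorrhage share, a subtype effect of 0 to 2 points and 20% explained variance, the two models disagree on non-inferiority in roughly 1% to 4% of trials. At zero true difference, rates near 8% need extreme inputs and should not be taken as the expected size. Disagreement is also more frequent if the true difference lies between zero and the margin. The rise in false non-inferiority to at most about 3.5% occurs only if the model is chosen after both results are seen, and the documents give no sign that this is intended. The point should be settled before unblinding because the model decides the trial and settling it is nearly free.

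**What to change.** Before unblinding, state one covariate list for the primary ANCOVA and use it in both the key-covariates and the primary-analysis paragraphs.

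- **Preferred:** add stroke subtype (ischemic or intracerebral hemorrhage) to the primary ANCOVA, which carries out what the key-covariates paragraph already says, and keep the four-covariate model as a sensitivity analysis.
- **Alternative:** if the sponsor prefers four covariates, remove or relabel the subtype sentence in the key-covariates paragraph.
- **Section 8.4:** apply the same subtype decision, but do not simply point to the primary list, because that would leave baseline FM as the only severity covariate. Replace it with, or add to it, each endpoint's own starting value: Box & Blocks at Screening and SIS-Hand at Baseline. Section 8.5 already does this for the knowledge exam and PACES.
- **Scope:** say in the key-covariates paragraph which analyses its list covers, since the 8.5 models differ from it.

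The cost is a few phrases and, if subtype is added, one degree of freedom (112 to 111). Simulated power falls by about half a point if subtype has no effect and rises if it is prognostic; the largest gain seen, 4.4 points, belongs to the large-effect end of the assumed range. No new data should be needed, because inclusion criterion 2 requires the stroke type to be established. The schedule in section 5.3 has no separate subtype item, so the sponsor should confirm that it is recorded in the database.

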### 5.3.1 Screening Visit

The Screening Visit occurs 3 weeks to 35 weeks after the date of stroke onset. The study site will call the subject 1-2 days before the Screening Visit, reminding the patient of the time and place of the visit. Prior to signing informed consent, the subject will be given the opportunity to become familiar with the Box & Blocks kit, and will be given the option to test him/herself given that only those persons who can score at least 3 blocks in one minute will be potentially eligible.

All procedures at the Screening Visit will be performed by one of the site's certified Assessment Therapists; in selected cases and with prior approval from the overall study PI ([name]), a site may request to have a different member of the research team be trained, certified and approved for performing selected assessments. For a given patient, all assessments should be performed by the same Assessment Therapist, as reasonably possible, across the Screening, Baseline, Post-Therapy, and Day 30 Follow Up Visits.

The study will be explained to the subject, after which the subject will be asked to sign informed consent. Next, screening for eligibility will ensue, including medical history, Fugl-Meyer test, Visual Acuity, Box & Blocks test, Montreal Cognitive Assessment, the 3 rehabilitation exercise test examples (used to insure that the subject is able to successfully follow instructions), and the Geriatric Depression Scale (GDS). Other measurements at this visit will include the modified Ashworth Spasticity Scale of the wrist, the Nottingham Sensory Scale, blood pressure, weight, the modified Rankin Scale, the NIH Stroke Scale, and the Stroke Knowledge Exam. The amount of any therapy (OT, PT, SLT) that the subject received since the time of stroke onset and prior and concomitant medications will be documented. Note that the Screening Visit assessments, with the exception of the Fugl-Meyer test, may be completed thereafter up to and including at the Baseline Visit. This is not encouraged but it is recognized that this may be useful for selected patients.

Subjects deemed eligible at the end of Screening Visit will be given the time and date of the Baseline Visit.

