**Determination of sample size:**

The objective of this study is to assess comparable efficacy of telerehabilitation vs. in-clinic intensive arm motor rehabilitation therapy with respect to the mean  $\Delta_{FM}$  from the Baseline Visit to the 30 Day Follow Up Visit, using a non-inferiority margin of 2.05. Based on our pilot study, the mean  $\Delta_{FM}$  in the telerehabilitation group is expected to be 4.80 with SD=3.80; extension to multiple sites and enrollment of subjects at earlier time points post-stroke may be associated with larger variance, and so a SD=4.0 is assumed. Comparable efficacy will be established provided that the lower bound of the 95% confidence interval for the difference in the  $\Delta_{FM}$  between treatment groups is greater than -2.05. Assuming 80% power, the study will therefore seek to attain 30 Day Follow Up data on N=124 subjects (62 per arm). If the dropout rate is as high as 20%, then as many as 155 subjects may need to be enrolled.

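### The primary ANCOVA adjusts for only the second of two pre-randomization Fugl-Meyer scores; adding the Screening score is an optional, almost free gain in precision of uncertain size, not the correction of an error

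*Combined protocol and SAP*

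**What the plan says.** The endpoint is defined in Section 8.3: "The primary outcome measure is the within-subject change in arm motor FM score from Baseline Visit to 30 Day Follow Up Visit". The primary efficacy analysis is an ANCOVA of that change, "adjusting for days from stroke onset to randomization, FM score at Baseline Visit, age, and enrollment site". The key covariate list in 8.3 likewise names FM at the Baseline Visit and no other FM score. Section 5.2 balances randomization on the Baseline Visit score only.

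Two readings exist for every eligible subject, because Section 13.2 requires "Arm motor FM score of 22-56 (out of 66) at both the Screening Visit and Baseline Visit". They come from separate visits: Section 5.3 places Baseline 1-21 days after Screening (target 7), and Section 5.3.1 makes FM the one screening assessment that may not be put off to Baseline. On raters, 5.3.1 says "For a given patient, all assessments should be performed by the same Assessment Therapist, as reasonably possible", and Section 11.2 requires FM certification, renewed every four months.

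Screening data are used elsewhere. Section 5.3.3 feeds Screening and Baseline data into therapy planning, and Section 8.1 bases multiple imputation on all available evaluation data. Screening FM is not named as a covariate in any analysis model.

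**The concern.** The change score subtracts one Baseline reading, so the error in that reading enters the outcome. Adjusting for the same reading recovers little of it when subjects differ widely at entry (the pilot baseline SD was 12, Section 3). A second reading taken before assignment carries further information about true baseline status and could narrow the confidence interval.

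Width matters because the non-inferiority decision rests on one confidence bound against a 2.05-point margin, and planned power has little reserve above 80%. The SD of 4.0 is a modest increase on 3.80 from a 12-subject pilot, and the sample size section itself expects that more sites and earlier enrolment may raise the variance.

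**Working it through.** **Inputs from the documents.** Two-sided alpha 0.05 (Section 8); sample size "using a non-inferiority margin of 2.05"; "so a SD=4.0 is assumed" for the change; 62 per arm, 80% power and 20% dropout (sample size paragraph); 1:1 allocation (5.3.2).

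**Assumed, because the documents do not give them.** A true difference of 0; a single-test FM error SD, s, of 1, 1.5 or 2; a true-score SD of 10 (8 and 12 give nearly the same results); any real change (drift) between the two visits; and any share of error common to all visits.

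**The plan's own figure.** n per arm = 2 × 4.0² × (1.96 + 0.842)² / 2.05² = 59.8, so 60. The noncentral t gives 61, against 62 stated. Power at 62 per arm: the standard error is 4.0 × √(2/62) = 0.718, and Φ(2.05/0.718 − 1.96) = 81.4% (80.8% by t). Enrolment: 124/0.8 = 155. The plan's size reproduces, with no credit taken for any covariate.

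**Effect of a second reading.** Let B and S be the Baseline and Screening scores, vT = 100 the true-score variance at Screening, d the drift SD, and ρ the correlation of drift with later true gain. Let u and h be the visit-specific and shared error variances, with u + h = s². Change variance is held at 16, so the variance of true gain is vG = 16 − 2u.

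- Cov(change, B) = ρ·d·√vG − u; Cov(change, S) = 0.
- Var(B) = vT + d² + s²; Var(S) = vT + s²; Cov(B, S) = vT + h.
- Residual variance with B alone = 16 − Cov(change, B)² / Var(B).
- With B and S = 16 − Cov(change, B)² × Var(S) / [Var(B)·Var(S) − Cov(B, S)²].

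*Example, s = 1.5, no drift, independent errors.* u = 2.25. B alone: 16 − 5.0625/102.25 = 15.95. B and S: 16 − 5.0625 × 102.25/(102.25² − 100²) = 14.86. The reduction is 1 − 14.86/15.95 = 6.8%. Power moves from Φ(2.05/√(15.95 × 2/62) − 1.96) = 81.5% to Φ(2.05/√(14.86 × 2/62) − 1.96) = 84.2%.

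Reduction in residual variance, with power after adding S in brackets (B alone gives 81.4-82.0% throughout):

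| Scenario | s = 1 | s = 1.5 | s = 2 |
|---|---|---|---|
| No drift, independent errors | 3.1% (82.6) | 6.8% (84.2) | 11.9% (86.3) |
| Drift SD 1, uncorrelated with gain | 2.0% (82.2) | 5.5% (83.6) | 10.5% (85.8) |
| Drift SD 1, ρ = +0.3 | 0.0% (81.4) | 1.7% (82.1) | 6.5% (84.1) |
| Drift SD 2, ρ = +0.3 | 1.5% (82.0) | 0.0% (81.4) | 2.5% (82.5) |
| No drift, half the error shared | 1.6% (82.0) | 3.5% (82.8) | 6.1% (83.8) |
| Drift SD 1, ρ = −0.3 | 9.2% (85.0) | 11.7% (86.1) | 15.4% (87.8) |

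Outside this range of s, with baseline SD 12, no drift and independent errors, the reduction is 0.8% at s = 0.5 and 18.6% at s = 2.5.

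**If the change SD is larger than planned.** At an illustrative 4.5, power at 62 per arm is about 72%; a 7-12% variance reduction would bring it to about 75-77%.

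**Validity.** A simulation of 3,000 trials per scenario, with the 22-56 entry rule on both scores, gave a bias below 0.015 points in size for both models. Rejection rates at the margin were 0.022 to 0.032, against a nominal 0.025 with a simulation standard error of √(0.025 × 0.975/3,000) = 0.003. The highest rate, 0.032, came from the two-covariate model with drift; Baseline alone gave 0.028 in that scenario.

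**The case against.** The strongest reply is that nothing is wrong with the plan. ANCOVA of change on the endpoint's own baseline is prespecified and valid, it matches the randomization balancing, and it meets its power target. That stands in full.

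Three points about size also stand.

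- The documents give no FM test-retest error, so the gain rests on an outside assumption.
- Zero drift fits this population poorly. Subjects may be screened three weeks after stroke, the visits may be three weeks apart, and Section 2.1 itself refers to weeks of spontaneous recovery. Drift that continues into later gain can cancel the benefit.
- A rater's stable scoring habit is common to all visits when the same therapist is used. It already cancels in the change score, and Screening FM cannot reduce it.

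Even in the best case the second score removes only about half of the Baseline error and none of the Day 30 error.

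What does not stand is that these points argue against the covariate. In this large-sample model it never raises residual variance, so the worst case is one degree of freedom spent for nothing.

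A reader might infer more than the documents support. Error in a single baseline score does not bias the treatment contrast, because assignment is randomized. The trial is not underpowered on its own assumptions. And Screening FM is not purely an entry gate, given its possible roles in therapy planning and imputation.

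**Conclusion.** The point holds as an optional, nearly free improvement in precision. Two pre-randomization FM scores exist for every eligible subject and the primary model uses one. With an assumed error SD of 1-2 points and change SD 4.0, the variance reduction is about 3-12% in the favorable case (no drift, independent errors). It is about 0-6.5% if drift is positively correlated with later gain or half the error is shared. Power at 62 per arm and a true difference of zero goes from about 81% to between 81% and 86%. Negatively correlated drift or a larger error SD would give more, but the documents offer no basis for relying on either. The powers of 84% and 86% belong to the favorable case at s = 1.5 and 2 and should not be read as expected values.

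**What to change.** Keep the endpoint as change from the Baseline Visit to the 30 Day Follow Up Visit. Before unblinding, so that the choice cannot look data-driven, add FM score at the Screening Visit next to FM score at the Baseline Visit in both the key covariate list and the primary efficacy analysis of Section 8.3. Do not average the two scores as the change-score baseline, since that would alter the endpoint.

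State that the addition applies to the FM model only. Section 8.4 analyses Box & Blocks and the Stroke Impact Scale hand domain in the same way as the primary outcome, so without that sentence the covariate might be carried over unintentionally.

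Naming Screening FM in the imputation model would only clarify Section 8.1, which already draws on all available evaluation data.

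The cost is a few words of SAP text and one degree of freedom, with no new data, visits or subjects. The gain may be close to zero, so leaving the model as it stands is also defensible.
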